#### **9.3.10.1 Analysis**

Pairwise comparison as Cochran Mantel Haenszel test adjusted by prior surgery will be applied to the proportion.

## **10. SAFETY**

All safety analyses will be performed for the Safety Analysis Population.

### **10.1 Adverse Events**

Adverse events (AEs) will be coded and classified by System Organ Class (SOC) and PT using MedDRA Version 23.0. Unless otherwise specified, analyses will be based on

treatment-emergent adverse events (TEAEs), which is any AE reported after the first dose of the study drug.

The number and proportion of patients who experienced at least 1 TEAE will be summarized by treatment group. The proportions will be presented along with the 95% CIs, calculated with the Clopper-Pearson method. The number of TEAEs reported will also be calculated. TEAEs with an outcome of death, other serious treatment-emergent adverse events (STEAEs), severe TEAEs, TEAEs leading to discontinuation of the study drug, treatment-related TEAEs, treatment-related TEAEs with an outcome of death, other treatment-related STEAEs, severe treatment-related TEAEs, and treatment-related TEAEs leading to discontinuation of the study drug will be summarized in the same manner. The definitions of these events are shown in Table 3.

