8.3 Adverse Events and Serious Adverse Events

The definitions of an AE and an SAE can be found in [Appendix 3](#).

Adverse events reported by the patient (or, when applicable, by a caregiver, surrogate, or the patient's legally authorized representative) must be captured in source documents. Abnormal laboratory test results, blood pressure, pulse rate, and ECG findings after the first dose that are considered to demonstrate a clinically significant change from baseline will be recorded in the eCRF as treatment-emergent adverse events (TEAEs).

The investigator and any qualified designees are responsible for detecting, documenting, and recording events that meet the definition of an AE or SAE and remain responsible for following up AEs that are serious, considered related to the study treatment or study procedures, or caused the patient to discontinue study treatment or withdraw from the study (see [Section 7](#)).

8.3.1 Time Period and Frequency for Collecting Adverse Event and Serious Adverse Event Information

All AEs/SAEs will be collected from the date of signing of the ICF until the End-of-study Visit at the time points specified in the SoA ([Section 1.3](#)).

All SAEs will be recorded in the eCRF and reported to the CRO within 24 hours of awareness, as indicated in [Appendix 3](#). The investigator or qualified designee will submit any updated SAE information to the CRO within 24 hours of awareness.

The investigators or qualified designees are not obligated to actively seek AEs or SAEs after conclusion of the study participation. However, if the investigator or qualified designee learns of any SAE, including a death, at any time after a patient is no longer in the study, and the investigator or qualified designee considers the event to be reasonably

related to the study treatment or study participation, the investigator or qualified designee must promptly notify the CRO via phone, e-mail, or fax (see [Appendix 3](#)). Investigator assessment of causality must be included with all SAEs reported to the CRO. Serious adverse events with missing investigator causality will be followed up urgently until provided to the CRO.

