9.4.6 Safety Analyses

All safety analyses will be performed on the Safety Population.

Adverse events will be classified by system organ class and preferred term using Medical Dictionary for Regulatory Activities (MedDRA). Adverse events reported after the initial dose of study drug will be considered TEAEs and will be analyzed.

The number and the percentage of patients who experienced TEAEs will be summarized by treatment group. Treatment-emergent SAEs, AEs related to study treatment, and TEAEs leading to discontinuation of study drug will also be summarized by treatment group. The number of occurrences of TEAEs, which are counted among patients reporting those TEAEs, will also be presented in the categories above in an overall summary.

For the summary of TEAEs by system organ class and preferred term, the number and percentage of patients who experienced TEAEs will be presented for each treatment group. A summary of TEAEs by severity and by relationship to study treatment will be presented by system organ class, preferred term, and treatment group.

All AEs, including AEs that have occurred before and after the first dose of the study treatment, will be listed.

Summary statistics for laboratory tests and vital signs will be presented for all time points. The change from baseline to each time point in laboratory tests and vital signs will be summarized. In addition, the proportion of patients with clinically significant changes from baseline in laboratory tests, vital signs, and ECG data will be presented. Criteria for clinically significant changes in laboratory tests, vital signs, and ECG data will be defined in the SAP.

Summary statistics for NPRS, COWS, and intraoperative and postoperative MME opioid dose will be presented for all time points. The COWS score in each domain will be summarized categorically. The opioid dose recorded in the eCRF will be converted to the MME opioid dose using conversion factors. The details will be defined in the SAP.

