
• Any abnormal laboratory test results (hematology or clinical chemistry) or other safety assessments (eg, ECG, radiological scans, vital signs measurements), including those that worsen from baseline, considered clinically significant in the medical and scientific judgment of the investigator (ie, not related to progression of underlying disease).• Exacerbation of a chronic or intermittent preexisting condition including an increase in frequency and/or intensity of the condition.• New conditions detected or diagnosed after study treatment administration even though they may have been present before the start of the study.• Signs, symptoms, or the clinical sequelae of a suspected drug-drug interaction.• Signs, symptoms, or the clinical sequelae of a suspected overdose of either study treatment or a concomitant medication. Overdose per se will not be reported as an AE/SAE unless it is an intentional overdose taken with possible suicidal/self-harming intent. Such overdoses should be reported regardless of sequelae.• “Lack of efficacy” or “failure of expected pharmacological action” per se will not be reported as an AE or SAE (unless fatal). Such instances will be captured in the efficacy assessments. However, the signs, symptoms, and/or clinical sequelae resulting from lack of efficacy will be reported as an AE or SAE if they fulfil the definition of an AE or SAE.• The signs, symptoms, and/or clinical sequelae resulting from lack of efficacy will be reported as an AE or SAE if they fulfil the definition of an AE or SAE.

Events NOT Meeting the AE Definition

- Any abnormal laboratory findings or other abnormal safety assessments which are associated with the underlying disease, unless judged by the investigator to be more severe than expected for the patient's condition.
- The disease/disorder being studied or expected progression, signs, or symptoms of the disease/disorder being studied, unless more severe than expected for the patient's condition.
- An elective procedure not reflecting a worsening of a known underlying medical condition is not considered an AE, and therefore will not be considered an SAE despite requiring hospitalization. However, complications of a procedure will be considered an AE and may be considered an SAE if hospitalization is prolonged (or any other SAE criterion is met).

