10.3.2 Recording and Follow-up of Adverse Events and Serious Adverse Events

AE and SAE Recording

- When an AE/SAE occurs, it is the responsibility of the investigator to review all documentation (eg, hospital progress notes, laboratory reports, and diagnostics reports) related to the event.
- The investigator will then record all relevant AE/SAE information in the eCRF.
- It is **not** acceptable for the investigator to send photocopies of the patient's medical records/discharge summary to the CRO in lieu of completion of the AE/SAE CRF page.
- There may be instances when copies of medical records for certain cases are requested by the CRO. In this case, all patient identifiers, with the exception of the patient number, will be redacted on the copies of the medical records before submission to the CRO.
- The investigator will attempt to establish a diagnosis of the event based on signs, symptoms, and/or other clinical information. Whenever possible, the diagnosis (not the individual signs/symptoms) will be documented as the AE/SAE.

Assessment of Intensity

The investigator will make an assessment of intensity for each AE and SAE reported during the study and assign it to 1 of the following Common Terminology Criteria for Adverse Events (CTCAE) Version 5.0 grades

(https://ctep.cancer.gov/protocolDevelopment/electronic_applications/ctc.htm#ctc_50):

- Grade 1 Mild; asymptomatic or mild symptoms; clinical or diagnostic observations only; intervention not indicated.
- Grade 2 Moderate; minimal, local or noninvasive intervention indicated; limiting age-appropriate instrumental activities of daily living (ADL)*.
- Grade 3 Severe or medically significant but not immediately life-threatening; hospitalization or prolongation of hospitalization indicated; disabling; limiting self care ADL**.
- Grade 4 Life-threatening consequences; urgent intervention indicated.
- Grade 5 Death related to AE.
 - * Instrumental ADL refer to preparing meals, shopping for groceries or clothes, using the telephone, managing money, etc.
 - ** Self care ADL refer to bathing, dressing and undressing, feeding self, using the toilet, taking medications, and not bedridden.
- An event is defined as serious when it meets at least 1 of the predefined outcomes as described in the definition of an SAE, NOT when it is rated as Grades 3, 4, or 5.
- The highest severity during the period in which the AE occurred will be recorded in the eCRF.

Assessment of Causality

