## 2. OVERVIEW

This is a Phase 2, multicenter, randomized, parallel-group, double-blind, placebo-controlled study in patients undergoing partial small or large bowel resection with primary anastomosis or radical cystectomy requiring bowel transection with primary anastomosis.

The study will consist of 3 study periods:

- a Screening/Baseline period (Day -14 to Day 0)
- a Treatment period (study treatment for no more than 11 days, including Day 0 [day of surgery] plus through 10 postoperative days).
- a Follow-up period 30 days after Day 10 or after the day of discharge (whichever is sooner), with a window of + 3 days, but not < 30 days (End-of-study Visit) or an Early Termination (ET) Visit.

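### TEAEs are classified by when an AE is reported, with no onset or worsening rule, so some AEs that began before dosing are counted and some post-dose worsening can be missed

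*SAP*

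**What the plan says.** The two definitions agree. SAP 10.1 bases its AE analyses on TEAEs and describes a TEAE by the clause "which is any AE reported after the first dose of the study drug". Protocol 9.4.6 states: "Adverse events reported after the initial dose of study drug will be considered TEAEs and will be analyzed".

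Four other provisions bear on how that rule works:

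- **Collection window.** Protocol 8.3.1: "All AEs/SAEs will be collected from the date of signing of the ICF until the End-of-study Visit". Screening runs from Day -14 to Day 0 (protocol 4.1, SAP section 2), so AEs can be on file up to 14 days before the first dose.
- **Severity.** Protocol 10.3.2: "The highest severity during the period in which the AE occurred will be recorded in the eCRF".
- **Worsening of known conditions.** Protocol Appendix 3 lists among the events that are AEs: "Exacerbation of a chronic or intermittent preexisting condition including an increase in frequency and/or intensity of the condition".
- **Conditions found later.** The same list includes: "New conditions detected or diagnosed after study treatment administration even though they may have been present before the start of the study".

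Neither document defines a TEAE by onset date or time, says whether a worsened AE gets a new record, or gives a rule for a missing onset time. SAP 6.4 says that missing values are not imputed.

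**The concern.** The date on which an event is reported is not the date on which it began or got worse. Because AE collection starts before dosing, a rule keyed to reporting can go wrong in both directions. It can admit events that predate the drug, and it can exclude deterioration that followed the drug.

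The stake is that one sentence governs the AE comparison. Every row of SAP Table 3 (fatal, other serious, severe, leading to discontinuation, treatment-related) starts from a TEAE. The SOC and preferred-term tables and the severity plots do too, and gastrointestinal disorders are one of the two groups that SAP 10.1 singles out for plotting. In a dose-ranging study planned for 50 to 85 patients per group, a few misclassified patients can change how a table reads.

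**Working it through.** The plan gives no figure that depends on this definition, so there is nothing to reproduce. The check has two parts: run typical cases through the text, then ask what each error would do to an arm comparison.

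**Cases under the rule as written**

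| Case | Result | Basis |
|---|---|---|
| Onset between consent and first dose, first reported after dosing | Counted as a TEAE | SAP 10.1, protocol 9.4.6 |
| Symptom recorded before dosing, worsens later, original record updated | Can be left out | Reported before dosing; 10.3.2 enters one highest severity; no rule requires a new record |
| Chronic or intermittent pre-existing condition worsens, entered as a new AE after dosing | Counted | Appendix 3 |
| Clinically significant laboratory, blood pressure, pulse or ECG change from baseline after dosing | Counted | Protocol 8.3 |
| Condition first detected after dosing that may have been present earlier | Counted, as the protocol intends | Appendix 3 |
| Known condition that only fluctuates and does not worsen | Not an AE, not counted | Appendix 3 |

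The first two rows are the problem. The second is a possibility, not a certainty. Appendix 3 points towards a new entry for a worsened chronic condition and 10.3.2 allows one record to absorb the worsening, so sites could treat the same event differently.

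**Day 0.** The first dose is given 30 minutes to 6 hours before the scheduled start of surgery (protocol 4.1). SAP Table 1 divides Day 0 only into before and after surgery. The before-surgery slot therefore contains both pre-dose and post-dose time, and the visit label cannot separate them. Onset time relative to the dose can.

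**Direction of each error.** Let p0 and p1 be the correct event proportions on placebo and on a naldemedine dose.

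- *Late reporting at the same rate L in both arms*, in patients who would not otherwise be counted: the difference is (p1 + L) - (p0 + L) = p1 - p0, unchanged in expectation. The ratio (p1 + L)/(p0 + L) moves towards 1.
- *Lost worsening* at rates w0 and w1: the difference becomes (p1 - p0) - (w1 - w0). It shrinks if worsening is commoner on the drug.

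**Illustration.** All counts here are assumed; none is in the documents. Take 50 patients per arm and one event type. Post-dose onset is 2 on placebo v 5 on 5 mg, post-dose worsening of a recorded pre-dose AE is 0 v 2, and late-reported pre-dose onset is either 0 or 3 in each arm.

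| Scenario | Placebo | 5 mg | Difference | Ratio |
|---|---|---|---|---|
| Correct: 2 v 5 + 2 | 2/50 = 4% | 7/50 = 14% | 10 points | 3.5 |
| Worsening lost only | 2/50 = 4% | 5/50 = 10% | 6 points | 2.5 |
| Late reports added only | 5/50 = 10% | 10/50 = 20% | 10 points | 2.0 |
| Both | 5/50 = 10% | 8/50 = 16% | 6 points | 1.6 |

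The whole fall from 10 to 6 points comes from the lost worsening. Equal late reporting affects only the ratio.

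**The case against.** The case on the other side is that this is loose wording with limited consequences. Much of it stands.

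- *'Reported' may simply mean 'occurring'.* Protocol 9.4.6 itself refers, when describing the listing, to AEs that occurred before and after the first dose. This is plausible, but neither definition says it, and a worsening clause would still be missing.
- *Worsening is already covered.* This stands for laboratory, blood pressure, pulse and ECG findings. Protocol 8.3 makes clinically significant post-dose changes TEAEs, and 8.2 requires results abnormal at baseline that significantly worsen to be reassessed. A reader might offer a low pre-dose potassium that falls further as an example of a lost event; the documents do not support that. It also stands for chronic or intermittent conditions entered as new AEs. It does not clearly reach an acute symptom already recorded during screening.
- *A single record is inferred.* This stands. Section 10.3.2 says which grade to enter and does not forbid a new record. The eCRF completion guideline is not available here, so onset time may already be captured.
- *Serious events would resurface.* A reader might infer that worsening vanishes from every TEAE table, including the serious rows. An event that becomes serious after dosing must be reported as an SAE within 24 hours (protocol 8.3.1, 10.3.3), and that can be read as a report after the first dose. The exposed summaries are chiefly the overall, severe and discontinuation ones.
- *Old conditions are not swept in generally.* This stands. Past and current conditions are recorded as medical history at screening (Schedule of Activities, footnote d), non-worsening ones are not AEs, and counting newly detected conditions is the protocol's own choice. What is left is onset between consent and first dose.
- *Other safety outputs do not use the TEAE flag.* This is true of the full AE listing, the laboratory and vital-sign criteria, ECG, NPRS and COWS summaries, and the DMC's review. None replaces the TEAE tables for symptoms.

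**Conclusion.** The point holds in a limited form. Applied literally, the definition counts AEs that began between consent and first dose but were first reported afterwards. It can also omit a symptomatic AE, recorded before dosing, that worsens on its original record. The first consequence follows directly from the text. The second depends on how sites handle records, which the documents leave open.

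The size cannot be estimated, because the documents give no pre-dose AE rates and no rates of late reporting or worsening. The illustration shows direction only. It would be wrong to conclude that both errors narrow the risk difference. Late reporting at equal rates leaves the expected difference alone and dilutes the ratio. Only lost worsening that is commoner on the drug reduces the difference.

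The change is worth making because the definition underlies all TEAE tables and the remedy is cheap. Protocol 9.4 has the SAP finalized before unblinding and database lock, which is the point by which the definition should be settled.

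**What to change.** 1. In SAP 10.1 and protocol 9.4.6, use one definition: a TEAE is an AE with onset date and time at or after the first dose, or with onset before it and an increase in severity or seriousness after it.
2. In protocol 10.3.2, state that an AE ongoing at first dose which then worsens is entered as a new record, with the onset time of the worsening.
3. For Day 0, classify by onset time relative to the first dose. Treat AEs with a missing onset time on that day as treatment-emergent, and state this as an exception to the no-imputation rule in SAP 6.4.

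The cost is a few sentences across the two documents and the eCRF guidance, plus a small amount of extra data entry for pre-dose AEs that worsen. Sample size, visits and the efficacy analyses are unaffected.

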**Table 3** **Definition of Adverse Event Terms**

Term	Definition
TEAE with an outcome of death	TEAE with “Fatal” in terms of outcome
Other STEAE	TEAE with “Serious” in terms of seriousness excluding TEAE with an outcome of death
TEAE leading to discontinuation of the study drug	TEAE with “Drug withdrawn” in terms of the action taken for study drug
Severe TEAE	TEAE with “Severe” in terms of severity
Treatment-related TEAE	TEAE with “Related” in terms of the causal relationship with study drug
Treatment-related TEAE with an outcome of death	Treatment-related TEAE with “Fatal” in terms of outcome
Other treatment-related STEAE	Treatment-related TEAE with “Serious” in terms of seriousness excluding treatment-related TEAE with an outcome of death
Severe treatment-related TEAE	Treatment-related TEAE with “Severe” in terms of severity
Treatment-related TEAE leading to discontinuation of the study drug	Treatment-related TEAE with “Drug withdrawn” in terms of the action taken for study drug

STEAE = serious treatment-emergent adverse event; TEAE = treatment-emergent adverse event.

The number and proportion of patients who experience TEAEs will be summarized by SOC and PT for each treatment group. For these summaries, patients with multiple TEAEs will be counted only once within an SOC and PT. TEAEs with an outcome of death, other STEAE, TEAEs leading to discontinuation of the study drug, treatment-related TEAEs, treatment-related TEAEs with an outcome of death, and other treatment-related STEAEs will be summarized in the same manner.

TEAEs relating to opioid withdrawal defined in Table 4 will also be summarized.

The proportion of specific TEAEs relating to gastrointestinal disorders and opioid withdrawal defined in Table 4 and all TEAEs by severity will be plotted.

**Table 4      Definition of Specific TEAE**

Specific TEAE	Definition
Gastrointestinal disorders	All Preferred Terms under Gastrointestinal Disorders (SOC)
Opioid withdrawal	All Preferred Terms (Cholinergic rebound syndrome, Delusion of parasitosis, Drug rehabilitation, Drug withdrawal convulsions, Drug withdrawal headache, Drug withdrawal maintenance therapy, Drug withdrawal syndrome, Drug withdrawal syndrome neonatal, Rebound effect, Steroid withdrawal syndrome, Withdrawal arrhythmia, Withdrawal catatonia, Withdrawal syndrome) under Drug withdrawal (MedDRA SMQ)

The number and proportion of patients who experience TEAEs in each category of severity will be summarized by SOC and PT for each treatment group. Patients who experience the same TEAE more than once in different categories will be counted only once by the worst severity. Treatment-related TEAEs will be summarized in the same manner.

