Bone or Joint aches If patient was having pain previously, only the additional component attributed to opiates withdrawal is scored 0 not present 1 mild diffuse discomfort 2 patient reports severe diffuse aching of joints/muscles 4 patient is rubbing joints or muscles and is unable to sit still because of discomfort	Gooseflesh skin 0 skin is smooth 3 piloerection of skin can be felt or hairs standing up on arms 5 prominent piloerection	
Runny nose or tearing Not accounted for by cold symptoms or allergies 0 not present 1 nasal stuffiness or unusually moist eyes 2 nose running or tearing 4 nose constantly running or tears streaming down cheeks	Total Score _____ The total score is the sum of all 11 items Initials of person completing assessment: _____	

Score: 5-12 = mild; 13-24 = moderate; 25-36 = moderately severe; more than 36 = severe withdrawal

This version may be copied and used clinically.

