# **6. STATISTICAL CONSIDERATIONS FOR DATA ANALYSES AND HANDLING**

## **6.1 Statistical Reporting**

Unless otherwise noted, continuous variables will be summarized by using the number of nonmissing observations, arithmetic mean, standard deviation (SD), median, and minimum, and maximum values as summary statistics; categorical variables will be summarized by using the frequency count and the percentage of patients in each category.

Patient study data, including data not appearing in tables, will be presented in by-patient data listings. In general, all tables will be presented by treatment group. Individual patient data and any derived data will be presented by treatment and patient.

All analyses will be performed using SAS® Version 9.4 or higher (SAS Institute, Cary, NC, USA), or WinNonlin Version 6.2.1 or higher (Certara, St Louis, MO, USA).

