## 10.7 Clinical Opiate Withdrawal Scale

Total scores across all domains will be summarized using statistics for continuous variables on each day. The proportion of patients in each score category by domain will be calculated.

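### SAP Table 4 reports a generic drug-withdrawal term group as opioid withdrawal, and no table counts patients by COWS severity band

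*SAP*

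**What the plan says.** **Adverse events.** SAP 10.1, Table 4, sets up a specific adverse event called opioid withdrawal and fills it with all preferred terms of one SMQ. The printed list includes "Drug withdrawal maintenance therapy, Drug withdrawal syndrome, Drug withdrawal syndrome neonatal" and closes with "Rebound effect, Steroid withdrawal syndrome, Withdrawal arrhythmia, Withdrawal catatonia, Withdrawal syndrome) under Drug withdrawal (MedDRA SMQ". The text above that table says "TEAEs relating to opioid withdrawal defined in Table 4 will also be summarized", and it also plans a plot of the group's proportion.

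**COWS.** SAP 10.7 says "Total scores across all domains will be summarized using statistics for continuous variables on each day" and "The proportion of patients in each score category by domain will be calculated". SAP 6.1 defines the continuous statistics as the number of observations plus "arithmetic mean, standard deviation (SD), median, and minimum, and maximum values as summary statistics", and it also plans by-patient listings. Protocol 9.4.6 matches this: summary statistics at each time point, and "The COWS score in each domain will be summarized categorically".

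**Thresholds already in the protocol.** The COWS form in Appendix 9 grades the total: "Score: 5-12 = mild; 13-24 = moderate; 25-36 = moderately severe; more than 36 = severe withdrawal". Protocol 7.1 requires study treatment to stop when a COWS score exceeds 36 on any assessment day. The version history in Appendix 10 records that COWS was added at a regulator's request, to monitor for opioid withdrawal.

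**The concern.** Naldemedine blocks mu-opioid receptors and is given here to patients whose primary postoperative analgesia is opioid, so withdrawal is an obvious safety question. The daily doses are 2.5 to 10 mg (1.25 to 5 mg twice daily), against 0.2 mg once daily for the approved tablet, which is 12.5 to 50 times as much. Protocol 2.3 says that the risks in this population are not known.

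The two planned summaries that bear on the question each have a gap. The labelled adverse event group can count an event that is not opioid withdrawal. The dedicated instrument is never turned into a number of affected patients, although the protocol supplies both the bands and a threshold for doing so. With 44 to 85 patients per group, withdrawal would probably show as a few individuals. The natural summary is then a count per group, which the plan does not produce.

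**Working it through.** The plan states no figure on this point, so there is nothing to reproduce. The check is a reading of the lists, a sum, and one illustration.

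**1. The term list.** Table 4 prints 13 preferred terms. Terms naming opioids or opiates: 0. Terms naming another drug class: 1 (steroid withdrawal). Terms naming a population that cannot be enrolled: 1 (neonatal withdrawal; Protocol 5.1 admits ages 18 to 80). Two general terms, drug withdrawal syndrome and withdrawal syndrome, could hold a true opioid case. Steroid withdrawal is possible in this trial: Protocol 6.5 does not prohibit corticosteroids, and Protocol 5.2 excludes only complicated inflammatory bowel disease.

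**2. What the bands apply to.** Item maxima on the Appendix 9 form are pulse 4, GI upset 5, sweating 4, tremor 4, restlessness 5, yawning 4, pupils 5, anxiety 4, aches 4, gooseflesh 5, runny nose 4.

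4 + 5 + 4 + 4 + 5 + 4 + 5 + 4 + 4 + 5 + 4 = 48 over 11 items.

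Every band, and the threshold of 36, therefore refers to the total. Tables of single-item categories cannot be added up to give the distribution of totals, because they do not show which item scores belong to the same patient.

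**3. What the daily statistics show and do not show.** Assumption, for illustration only: *x* patients score 37 on a given day, all others score 0, and everyone is assessed. The mean is 37*x*/n. The proportion is *x*/n, with a Clopper-Pearson 95% interval.

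| n per group | x | Mean | Maximum | Above 36 | 95% interval |
|---|---|---|---|---|---|
| 44 | 1 | 0.84 | 37 | 2.3% | 0.06 to 12.0% |
| 44 | 2 | 1.68 | 37 | 4.5% | 0.6 to 15.5% |
| 50 | 1 | 0.74 | 37 | 2.0% | 0.05 to 10.6% |
| 50 | 2 | 1.48 | 37 | 4.0% | 0.5 to 13.7% |
| 85 | 1 | 0.44 | 37 | 1.2% | 0.03 to 6.4% |
| 85 | 2 | 0.87 | 37 | 2.4% | 0.3 to 8.2% |

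The maximum flags the event in every row but does not separate one patient from two. The means all lie below 5, where the mild band begins. In this artificial case a reader could work back from the mean to *x*, because every other score is 0. With ordinary variation in scores that is not possible. High maxima on two days could also come from one patient or from two, and daily tables do not say which.

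**4. Comparison within the SAP.** For laboratory tests, SAP 10.3 counts patients meeting preset criteria at each time point and also at least once during the study. Table 5 includes ALT or AST above 8 times the upper limit of normal, which is a stopping threshold in Protocol Appendix 5. The COWS threshold of 36 is likewise a stopping threshold, yet it has no such count.

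**The case against.** The strongest reply is that little is hidden.

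- **COWS extremes.** A reader might infer that COWS is reported only as means, so that a single severe case would go unseen. The documents do not support that. The minimum, maximum and SD are planned for each day and patient data are listed, so such a case would be visible. What stands is narrower: patients per band are not counted.
- **Adverse events.** A reader might infer that the opioid-withdrawal rate will be materially inflated. The documents do not show this either. SAP 10.1 tabulates all treatment-emergent events by preferred term, so a steroid-withdrawal event would appear under its own name. One event always contributes 1/n (2.0% at 50, 1.2% at 85); that is arithmetic, not an expected bias, and the documents give no likelihood. The neonatal term is merely irrelevant.
- **Missed cases.** Nor do the documents show that true cases would be lost, given the two general syndrome terms. A patient stopped for a high COWS score would also enter the table of events leading to discontinuation, if recorded as an adverse event with drug withdrawn.
- **Agreement with the protocol.** The SAP follows Protocol 9.4.6, and COWS is not a listed safety endpoint in Protocol Table 3-1. There is no departure from the protocol here.
- **Trimming the list.** Taking an SMQ whole and printing it is transparent. A hand-picked subset would be partly arbitrary and would still hold no opioid-specific term. This stands, and it makes relabelling the cleaner remedy.
- **Shift from baseline.** The Schedule of Activities places one COWS assessment before surgery on Day 0, but it does not order that assessment against the first dose, given 30 minutes to 6 hours before the scheduled start. SAP 6.5.2 takes baseline as the last value before randomization, which is also on Day 0. The pre-surgery score may therefore be post-dose. This stands, and it limits the fix.

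**Conclusion.** Both gaps are real and small. The Table 4 heading claims more specificity than its terms have, so a stated rule can count a non-opioid event as opioid withdrawal. The COWS plan lets a reader see that someone scored high on a given day, but not how many patients in each group reached a band or passed 36 over the study. The effect is on the labelling and completeness of safety reporting. The primary, secondary and exploratory efficacy analyses are untouched. The term count and the absence of a band table rest on the documents alone; the means and intervals rest on the stylised assumption stated with them and show only what each statistic can reveal. This is a minor improvement to make, not a defect that threatens a conclusion of the trial.

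**What to change.** Before unblinding, amend the SAP in two places.

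1. **Table 4.** Either rename the row *Drug withdrawal (SMQ)* and carry that name into the summary and plot, or remove from the opioid-withdrawal group the terms that name another drug class or population (steroid, neonatal). State the reason in either case.
2. **Section 10.7.** Add, by treatment group, the number and percentage of patients by worst post-dose COWS total, using the Appendix 9 bands with a row for totals below 5. The top band is already above 36. Show a shift from the pre-surgery score only for patients whose score was recorded before the first dose, and say how many that excludes.

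The cost is a wording change and one more descriptive safety table from data already collected. The shift display also requires checking the COWS time against the first-dose time. No clinical rule or efficacy analysis changes.
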